6.3.9 Biomarkers

All observed values will be listed for biomarkers, which may include osteopontin, IL-1 β , IL-2, IL-6, IL-10, TNF- α , CXCL10, troponin I (cardiac, fast skeletal, slow skeletal), troponin T, CK-MM, CK-MB, creatine kinase (total), creatine phosphate, creatinine, myostatin, and follistatin.

6.3.10 Resource Utilization

No endpoint-specific displays will be produced.

7 SAFETY ANALYSES

Listings and summaries of the safety parameters will be done for the Safety population. All summaries will be presented by treatment group. Safety parameters are described below.

7.1 Adverse Events

AEs will be coded using MedDRA coding system (Version 21.0). Potential primary safety endpoints, described in Section 2.2.1, will be adjudicated by an independent Clinical Events Committee (CEC).

The following AEs are defined as treatment-emergent AEs (TEAEs):

- AEs occurring after the initiation of the IV catheter placement for the initial dose of IP; or
- AEs with completely missing start date, or similarly, AEs that started the same month and year as IP administration but with missing start day.

Subject listings of all adverse events as reported will be provided. A separate listing will be done for TEAEs as adjudicated by the CEC. Serious AEs, primary safety endpoints as adjudicated, TEAEs adjudicated as related to IP or administration procedure, and hypersensitivity reactions as adjudicated will be listed separately.

All summary tables will be reported using TEAEs as adjudicated by the CEC. A summary of the primary safety endpoints will be presented. In addition, TEAEs related to IP or administration procedure and hypersensitivity reactions will be summarized.

AEs will be displayed by MedDRA SOC and PT, with subjects who have the same AE counted only once for that event and subjects who have more than one AE within a SOC counted only once in that SOC. The numbers and percentages of subjects reporting an event, as well as the number of events that were reported, will be calculated by treatment group.

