13.2.4. Reporting Adverse Events

All adverse events are collected from the time of signing informed consent for trial participation until completion of 12 months or early termination, whichever occurs first. All AEs occurring after the initiation of the IV catheter placement for the initial dose of IP will be considered treatment emergent. Any ongoing adverse event that has not been resolved at the time of trial completion or early termination for a subject will be marked as ongoing on the adverse event case report form (CRF).

All AEs will be entered into the electronic data capture (EDC) system by trained site personnel at the investigative site.

Expected and unexpected SAEs must be reported to Capricor and entered into the EDC system within 24 hours of discovery of the event. For events that do not have complete information available at the time of initial report, the investigative site will submit all available information at the time of the submission. All SAE Report Forms must be signed by an Investigator and submitted with available source documentation. All source documentation must be de-identified prior to submission.

Should access to the EDC system be unavailable, SAEs and subsequent follow-up information must be reported to Capricor, or designee, via:

- Email: [REDACTED]
- Fax: [REDACTED]

All SAEs must be reported to the respective IRB in accordance with the investigative site’s policies. Copies of the submission will be collected by Capricor.

All SAEs will be reported to the DSMB at least semi-annually, or more frequently at the discretion of the Medical Monitor.

Capricor will promptly upon discovery, report serious and unexpected adverse events for which there is a reasonable possibility that the investigative therapy (i.e. administration product and/or investigative product) caused the events, to the Food and Drug Administration (FDA) in accordance with 21 CFR 312.32 regulations and ICH E2A guidelines.

For trials conducted under an investigational new drug (IND) application, FDA regulations require reporting of any serious suspected adverse reaction that is unexpected according to the current Investigator’s Brochure. A serious adverse reaction is defined as any adverse event for which there is a reasonable possibility that the drug/biologic caused the AE. For the purposes of IND safety reporting, “reasonable possibility” means there is evidence to suggest a causal relationship

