14.4.2. Adverse Events

Directly observed and spontaneously reported AEs will be recorded from time of signing informed consent (SAEs only) through the end of the trial. AEs will be coded using MedDRA® (Medical Dictionary for Regulatory Activities), in which each reported event is mapped to a Preferred Term (PT) and a System Organ Class (SOC). A treatment-emergent AE (TEAE) will be defined as an AE that was not present prior to the initiation of line placement procedure for the IP infusion or was present but worsened in intensity or frequency. All reported AEs will be listed. Both TEAEs and non-TEAEs will be summarized, overall and by severity and relationship to the IP and IP administration procedure. For each SOC and PT within SOCs, the numbers and percentages of subjects reporting an event as well as the number of events that were reported will be calculated. Deaths, AEs that resulted in trial discontinuation, SAEs, and AEs within 24 hours of IP administration will be listed and summarized separately.

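### SAP 7.1 omits the worsening limb of Protocol 14.4.2's treatment-emergent definition and drops its non-TEAE summary, so a pre-dose AE that worsens on its existing record is tabulated nowhere

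*SAP*

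**What the plan says.** The Protocol defines treatment emergence twice.

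- Section 14.4.2 (Adverse Events, in the statistics chapter) counts an AE that was absent before line placement "or was present but worsened in intensity or frequency". It then states: "Both TEAEs and non-TEAEs will be summarized, overall and by severity and relationship to the IP and IP administration procedure".
- Section 13.2.4 (Reporting Adverse Events) states: "All AEs occurring after the initiation of the IV catheter placement for the initial dose of IP will be considered treatment emergent". It says nothing about worsening.

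SAP 7.1 has two limbs: "AEs occurring after the initiation of the IV catheter placement for the initial dose of IP", and "AEs with completely missing start date, or similarly, AEs that started the same month and year as IP administration but with missing start day". On outputs it says: "All summary tables will be reported using TEAEs as adjudicated by the CEC". It also provides listings of all AEs as reported. Addendum 3.1 moves the tables from adjudicated to raw TEAEs, without restating the definition or adding a non-TEAE table. SAP Section 8, which records departures from the Protocol's statistical methods, covers dropped endpoints and population changes but mentions neither point.

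The Protocol also gives two start points for AE collection. Section 13.2.4 says "All adverse events are collected from the time of signing informed consent for trial participation". Section 14.4.2 says AEs "will be recorded from time of signing informed consent (SAEs only", a parenthesis that limits the pre-dose record to serious events. The schedule of assessments (Protocol Table 3) marks AE collection at Screening and Baseline.

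SAP 2.2.2 sets the secondary safety endpoint as the incidence and severity of all AEs through 12 months. SAP 2.2.1 lists related TEAEs among the primary safety endpoints.

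**The concern.** The worsening limb exists because an infusion can aggravate something already present. If the analysis rule looks only at onset date, such an event depends on how the site recorded it. The non-TEAE summary in Protocol 14.4.2 would have caught whatever the TEAE rule missed; the SAP removes that as well. With both gone, one class of event has no count by arm, in a placebo-controlled trial whose primary objective includes safety. A reader of the report who relied on 14.4.2 would not know that the tables follow a narrower rule.

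**Working it through.** There is no plan figure to reproduce. The check is a comparison of the definitions, followed by a scale calculation.

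**1. The definitions as sets.** Let A be AEs with onset after first catheter placement, M the AEs captured by the missing-date rule, and W the AEs outside M with onset before catheter placement that worsen afterwards on the same record. Protocol 14.6.2 already contains the missing-date rule, so M belongs to both definitions.

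- Protocol 14.4.2 with 14.6.2: A + M + W
- SAP 7.1: A + M
- Difference: W

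Measured against 14.4.2, the SAP count can be equal or lower, never higher.

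**2. Which events fall in W.**

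| Case | Protocol 14.4.2 | SAP 7.1 |
|---|---|---|
| (a) Pre-dose AE, worsening kept on the same record | TEAE | Not a TEAE |
| (b) Pre-dose AE, worsening entered as a new AE dated after dosing | TEAE | TEAE |
| (c) Medical-history condition that worsens after dosing, dated at worsening (Protocol 13.2.1.1 makes it an AE) | TEAE | TEAE |
| (d) Pre-dose AE with start date wholly missing, or day missing in the month of IP | TEAE | TEAE |
| (e) AE starting after infusion 1 and worsening after a later infusion | TEAE | TEAE |

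Only (a) is lost. Neither Protocol 13.2.3, 13.2.4 nor 13.2.6 says whether worsening of an open AE updates the old record or opens a new one. Section 13.2.6 has ongoing AEs reviewed at each visit and followed to resolution, which is compatible with a single continuing record. SAP 7.1.1 also lets the CEC combine separately reported AEs into one, which could turn (b) into (a) in adjudicated data.

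**3. Where case (a) then appears.** It is in the listing of all reported AEs. It is in no summary table, because SAP 7.1 restricts them to TEAEs and Addendum 3.1 adds none for non-TEAEs.

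**4. Exposure window.** Consent to first catheter placement. Screening is up to 30 days before randomization, and dosing should follow within 14 days: 30 + 14 = 44 days. This is not a ceiling. Protocol 7.1 allows a longer delay after discussion, and Protocol 12.6 allows genetic testing (29 to 49 days) to precede the rest of screening.

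**5. Scale.** 20 subjects randomized 1:1 gives 20/2 = 10 per arm if the split is even. One subject is 1/10 = 10 percentage points. If the split were 12:8, it would be 1/12 = 8.3 or 1/8 = 12.5 points. The shift applies to a table row in which that subject is not already counted. No event rate is available, so this is a per-subject scale and not an estimate of the effect.

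**The case against.** The strongest reply is that the SAP invented nothing: its wording is nearly that of Protocol 13.2.4. A reader might infer that the SAP overrode a single Protocol rule. The documents do not support that. The Protocol contradicts itself, and the SAP took one side. What remains is that it took the narrower side, against the Protocol's own statistics section, without saying so.

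A reader might also infer that every AE starting before dosing and worsening after it disappears. That is too strong. Protocol 13.2.1.1 makes a worsened pre-existing condition an AE, and a worsening entered as a new event with a post-dose date is a TEAE under both rules. Case (a) also stays in the listings, which are readable with 20 subjects. Listings, however, give no incidence by arm.

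The restriction to SAEs before dosing, if followed, shrinks the problem: a non-serious pre-dose condition would have no AE record with an early onset, and its worsening would be a new AE.

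Nor do the documents support a claim of material bias in the primary safety endpoints. Under Protocol 13.2.2, a relationship rating normally needs the event to follow exposure, so a record with pre-dose onset will seldom be rated related, although a narrow route remains. SAEs and deaths are defined from baseline without a treatment-emergence condition, though SAP 7.1's sentence about all summary tables leaves it unclear how their table is built.

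**Conclusion.** The point holds in a limited form. Against Protocol 14.4.2, the SAP omits the worsening limb, omits the non-TEAE summary and declares neither in Section 8; the Addendum repairs neither. The consequence is confined to AEs with onset between consent and first catheter placement whose worsening stays on the same record. For these, TEAE-only tables fall short of the secondary endpoint of all AEs, and any error in the counts is downward.

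The number of such events cannot be known from the documents and may be zero. The figure of about 10 percentage points per affected subject rests on an assumed even split and on that subject not already being in the row. The conclusion also rests on pre-dose AEs having been recorded, as Protocol 13.2.4 and Table 3 require and 14.4.2 puts in doubt.

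**What to change.** - **SAP 7.1:** add a third limb for AEs present before first catheter placement that worsen in intensity or frequency afterwards. State how worsening is identified, and date the treatment-emergent event at the worsening, whether it sits on the old record or a new one.
- **Addendum 3.1:** apply the same definition to the raw TEAE tables.
- **Non-TEAE summary:** restore it as in Protocol 14.4.2, or declare its removal with a reason in SAP Section 8.
- **Protocol 13.2.4 and 14.4.2:** reconcile them on the TEAE definition and on whether all AEs or only SAEs are collected from consent. The synopsis reports twenty treated subjects and enrollment has ended, so this cannot change what was recorded before dosing. It settles how those records are to be read, and the study report should say which collection rule sites followed.

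The cost is one derivation rule, one extra table and a few sentences. No design element or efficacy analysis changes.

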5.6.3. Repeat Administrations

The other element of safety relevant for the proposed clinical trial and related to the planned dosing regimen, is the potential for an immune response to the allogeneic product, planned for repeated administrations. Several lines of evidence suggest that repeat administration of CAP-1002 should have low immunotoxicity risk in humans.

In fact, equivalent primary (i.e., after a first dose) and secondary (i.e. after a second dose) efficacy benefits (i.e., improvements in LVEF) were observed using allogeneic and syngeneic CDCs in this study. Furthermore, there was no evidence of an increased cellular or humoral immune memory response using allogenic compared to syngeneic CDCs.

██████████ Further information about the allergic reactions is found in the Investigator's Brochure and Section 13.2.1.3.

These collective data suggest that repeat administration of CAP-1002 should be reasonably safe in humans. However, the risk of severe allergic reactions should be minimized by administration of medications that will be determined by the Investigator based on the pre-treatment guidelines provided by Capricor (Section 21.2) and/or institutional protocols.

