14.4.1. Safety Endpoints

The incidence of the following events through the 12-month timepoint will be **primary safety endpoints**:

- Acute respiratory decompensation within 2 hours following IP administration
- Hypersensitivity reaction
- All-cause mortality
- Serious adverse events
- Treatment-emergent adverse events related to IP or administration procedure

- Immune sensitization syndrome

The incidence and severity of all AEs will be evaluated as the **secondary safety endpoint**.

Treatment groups will be summarized and compared by the incidence of each event type and by the subject event rate. Safety during the study will be monitored by the independent, unblinded DSMB. See Section 13.2 for more detail on AE data collection and processing.

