5.11 IP Administration

Details of IP administration will be listed. The number of subjects that completed IP infusion at each visit will be summarized. This is defined as subjects that completed (without interruption or syringe pump interrupted and restarted) both IP syringe administrations. For each visit, the total dose delivered (M cells) from both the first and second IP syringe administration, the number of patients who completed each IP syringe administration, reasons IP syringe was not completed, duration of IP administration (minutes), and total dose of IP syringe delivered (M cells) will be summarized. In addition, for the second IP syringe, the reasons the second IP syringe was not administered will also be summarized.

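### The adverse-event summaries pool up to four infusions with no infusion number or infusion denominator, so they cannot separate first-dose reactions from reactions that emerge on re-exposure

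*SAP*

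**What the plan says.** The primary objective (Protocol 6.1, SAP 2.1.1) is the safety and efficacy of CAP-1002 given every three months. SAP 3 plans four infusions, on Day 1 and at Months 3, 6 and 9. SAP 2.2.1 defines acute respiratory decompensation and hypersensitivity reaction by onset within 2 hours of an infusion. Protocol 5.6.3 names a safety question specific to this regimen: it "is the potential for an immune response to the allogeneic product, planned for repeated administrations". The same section goes on to the need to minimise severe allergic reactions.

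For analysis, Protocol 14.4.1 states: "Treatment groups will be summarized and compared by the incidence of each event type and by the subject event rate". SAP 7 sets the stratifier: "All summaries will be presented by treatment group. Safety parameters are described below". SAP 7.1 displays events by system organ class and preferred term, "with subjects who have the same AE counted only once for that event", and gives numbers of subjects "as well as the number of events that were reported, will be calculated by treatment group". It also says: "In addition, TEAEs related to IP or administration procedure and hypersensitivity reactions will be summarized". Listings are planned: "Subject listings of all adverse events as reported will be provided". Addendum 3.1 moves the summary tables to the raw treatment-emergent events and leaves the adjudicated data listed but not summarised. It adds no split by infusion.

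Exposure is tabulated separately, in SAP 5.11: "The number of subjects that completed IP infusion at each visit will be summarized".

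Protocol 14.4.2 also commits to listing and summarising separately the adverse events that fall in the 24 hours after an infusion. SAP 7.1 has no such display.

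**The concern.** When the regimen is repeat dosing of an allogeneic cell product, the informative safety contrast is between the first infusion and later ones. A reaction at infusion 1 in a previously unexposed subject means something different from a reaction that first appears at infusion 3 or 4. Pooling all infusions removes that distinction from the summary tables.

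Exposure may also differ between arms. Under Protocol 7.5 an acute toxicity ends the infusion and re-challenge is decided case by case. Under Protocol 8.4 a subject whose reaction prevents further infusions may remain in follow-up. Reactors can therefore have fewer infusions at risk, and an event total with no infusion denominator does not adjust for this.

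At stake is whether the planned summaries of the primary safety endpoints can address the part of the objective that concerns dosing every three months.

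**Working it through.** The plan states no figure on this point, so there is none to reproduce. The check is what the SAP 7.1 counting rule returns for different reaction patterns.

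**Inputs.** 20 randomised subjects, 1:1 (SAP 3.1), taken as 10 per arm because the actual split is not stated; four infusions per subject (SAP 3); subjects and events counted by treatment group only (SAP 7, 7.1). The reaction patterns and rates are assumptions for illustration.

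**1. Fixed patterns.** One arm, 10 subjects, four of whom react once each, all infusions given:

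| Pattern | Inf 1 | Inf 2 | Inf 3 | Inf 4 | SAP 7.1 row |
|---|---|---|---|---|---|
| All at infusion 1 | 4/10 | 0/10 | 0/10 | 0/10 | 4 subjects (40%), 4 events |
| All at infusion 4 | 0/10 | 0/10 | 0/10 | 4/10 | 4 subjects (40%), 4 events |
| One at each | 1/10 | 1/10 | 1/10 | 1/10 | 4 subjects (40%), 4 events |

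**2. Rates.** Let the reaction rate rise over infusions as 2%, 5%, 12%, 25%, independent within subject.
- P(any reaction) = 1 − 0.98 × 0.95 × 0.88 × 0.75 = 38.6%.
- Expected events = 10 × (0.02 + 0.05 + 0.12 + 0.25) = 4.4.
- The same rates in falling order give the same 38.6% and 4.4.
- A flat rate with the same P(any) is 1 − (1 − 0.3855)^(1/4) = 11.5% per infusion, with 40 × 0.1146 = 4.6 expected events.

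Rising, falling and flat rates are practically indistinguishable on either SAP 7.1 count.

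**3. Unequal infusions.** Suppose four subjects react at infusion 1 and have no more infusions, while the other six have all four.
- Infusions started = 10 + 6 + 6 + 6 = 28, so 4/28 = 14.3% per infusion.
- In an arm with four single reactions and no stopping, infusions started = 40, so 4/40 = 10.0%.

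Both arms show 4 subjects and 4 events. The completed-infusion count in SAP 5.11 is not the right denominator: an infusion ended early because of a reaction would not count as completed. Infusions started are needed.

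**4. What a by-infusion table could deliver.** With zero events, the exact two-sided 95% upper bound is 1 − 0.025^(1/n).
- n = 10: 30.8%. n = 6 (the denominator at infusion 4 in step 3): 45.9%.
- For 4/10 the exact interval is 12% to 74%.
- Power of an exact McNemar comparison of infusion 1 with infusion 4 within one arm of 10 (20,000 simulated runs) is about 1% for rates of 5% vs 25%, 8% for 10% vs 40%, and 27% for 5% vs 50%.

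The table would describe a pattern; it could not test one.

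**5. The 24-hour summary.** Protocol 14.4.2 promises it; SAP 7.1 does not contain it; SAP 8, which sets out planned analyses that will not be performed, does not mention it; Addendum 3.1 does not restore it. Even as promised, it is not split by infusion number.

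**The case against.** The strongest reply is that the information is not lost. SAP 7.1 plans separate listings of adjudicated primary safety endpoints, hypersensitivity reactions and related events. SAP 4 sorts listings by subject, visit and, where applicable, date and time. SAP 5.11 lists infusion details and summarises, by visit, completion and the reasons for non-completion. Infusions are about 90 days apart and these reactions start within 2 hours. With 20 subjects, a reader could probably match each reaction to its infusion by hand. This stands, provided the listings show onset times, which the text does not say. It limits the point to the summary tables: a reader might infer that the trial cannot show the pattern at all, or that fewer infusions in one arm would be invisible, and neither follows.

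Four other stronger readings are not supported.
- That once-per-subject counting is the fault. It is a standard convention, and the same section also counts events, which separates repeat reactors from single reactors. What is missing is the infusion stratifier and denominator.
- That the 2-hour reactions are the protocol's sensitization endpoint. Immune sensitization syndrome is separate: it needs onset at 24 hours or later and a rise in donor-specific antibodies, which are listed by subject and visit (SAP 5.7).
- That pooling to 40 infusions per arm gives usefully tighter bounds. With zero events the bound falls from 30.8% (n = 10) to 8.8% (n = 40) only if infusions are independent within subject, and it says nothing about trend.
- That no by-infusion table exists. The final table list (SAP Appendix F) is redacted, so one cannot be ruled out; the readable text describes none.

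It is also fair that safety has no formal tests (Protocol 14.4) and that a by-infusion table would rarely establish a trend. That argues against a test, not against showing the counts.

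**Conclusion.** The point holds for the summary tables. As described in the readable text, they pool up to four infusions, cannot separate first-dose reactions from those emerging on re-exposure, and do not adjust event totals for unequal numbers of infusions. Three quite different patterns give an identical row of 4/10 subjects and 4 events, and in the stopping example rates of 14.3% and 10.0% per infusion look the same.

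The illustration assumes 10 subjects per arm; the rate calculation also assumes independence between infusions. The identity of the rows in the fixed-pattern table needs no distributional assumption. No claim is made about how many reactions occurred or whether reactors in fact stopped.

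The unexplained loss of the Protocol 14.4.2 24-hour summary is a separate discrepancy between protocol and SAP. Overall this is an inexpensive improvement worth making, because it concerns primary safety endpoints and a risk the protocol itself names. It does not undermine the planned per-subject tables.

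**What to change.** Add one descriptive table to SAP 7.1 and Addendum 3.1, by arm and infusion (1 to 4), for hypersensitivity reaction, acute respiratory decompensation and adverse events within 24 hours of an infusion:

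- For each infusion, subjects with an event over subjects who started that infusion, with exact intervals if wanted.
- Total events per infusion started.
- A row for subjects not given that infusion because of an earlier reaction, since later denominators exclude them.
- Raw treatment-emergent events, with adjudicated status flagged. A table of adjudicated events alone would conflict with Addendum 3.1.
- Attribution only inside the defined 2-hour or 24-hour window, so that events weeks later are not credited to an infusion.

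Keep the per-subject tables. The 24-hour rows, with a matching listing, would also meet the Protocol 14.4.2 commitment; if that display is to be dropped, SAP 8 should say so and why. State in the listing specification that onset date and time are shown.

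The cost is one table and one listing, built from event onset times and infusion records that the plan should already hold. No dosing, re-challenge or withdrawal rule changes. The downside is small cells, so the table should be labelled descriptive and carry no trend test.
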